13.0 STATISTICAL CONSIDERATIONS

13.1 Study Design

This is a prospective multicenter, randomized, open-label, phase 2 study evaluating whether the addition of radiation therapy to immunotherapy improves tumor response rate compared to treatment with immunotherapy alone in patients with platinum ineligible/refractory metastatic urothelial cancer. Allocation to the two study arms will be performed using stratified randomization as described in Section 4.6. Patients will be randomized 1:1 to immunotherapy (Arm A) or to immunotherapy plus radiation (Arm B). This trial is a superiority trial with the primary endpoint of tumor response. One formal interim analysis will be conducted for futility after 50% of the patients have been followed for 6 months after randomization; accrual will not be suspended for the interim analysis.

13.2 Study Endpoints

13.2.1 Primary Endpoint

The primary endpoint is tumor response within 6 months of randomization. Tumor response is defined as a complete response (CR) or partial response (PR) as assessed by the treating physician using RECIST v1.1 criteria.

13.2.2 Secondary Endpoints

Tumor response using iRECIST: A patient will be determined to have a tumor response if they have a CR or PR as assessed using iRECIST by central review.

Progression-free survival (PFS): This will be the time from randomization until disease progression as assessed by the treating physician using RECIST 1.1 or death due to any cause. Patients who are alive and without documented progression will be censored at the time of last disease evaluation.

Overall survival (OS): This will be the time from randomization until death due to any cause. Patients who are not known to be dead at time of analysis will be censored at the time of their last follow-up.

Rate of treatment discontinuation at 1 year: The proportion of patients who discontinue their protocol directed treatment prior to one year from date of study registration will be determined. Patients who stop their protocol directed treatment for any reason prior to one year from study registration will be considered to have discontinued their treatment.

Adverse events: These will be assessed using CTCAE v5.0.

13.3 Subgroup Analysis

Subgroup analysis may be conducted in the following groups for efficacy endpoints including tumor response, PFS, and OS.

- 1) Platinum status: platinum ineligible versus platinum refractory
- 2) Visceral metastasis: present versus absent

13.4 Sample Size Calculation

The sample size was determined with nQuery (v8.6.1.0) under the following assumptions:

- 1) one-sided alpha = 0.10
- 2) power = 90%
- 3) arm A (control arm) tumor response rate = 20%
- 4) minimum detectable increase in response rate = 20% (absolute)
- 5) one interim analysis for futility after 50% of patients followed for response

This requires a total sample size = 136 evaluable patients (68 in each arm). The sample size will be inflated by 5% to account for ineligible or non-evaluable patients, so the target accrual is 144 patients.

13.5 Accrual time and study duration

The anticipated accrual rate is approximately 5 patients per month. The maximum expected accrual period is approximately 30 months (if trial is not stopped early for futility). Patients will be followed for tumor response for 6 months following randomization; therefore the maximum total study duration for the primary endpoint (including OS follow-up) approximately 36 months. Patients will be followed for PFS and OS for 3 years.

13.6 Primary Analysis Plan

Interim analysis for futility: There will be one interim analyses for futility. The interim analysis will occur after 50% of the patients (i.e. 68) have been followed for six months. If at this time the tumor response for Arm A (immunotherapy alone) is greater than the tumor response rate for Arm B (immunotherapy plus radiation), which would correspond to an OR > 1, the recommendation will be to stop the trial due to futility.

Final Analysis: The final analysis will occur after 136 evaluable patients have completed 6 months of follow-up. The tumor response rate will be analyzed with a Mantel-Haenszel test (that accounts for the randomization stratification factors) comparing the response rates between the two treatment arms. The analysis will be a modified intent-to-treat analysis where patients are ineligible or not evaluable will be excluded. An additional analysis will be conducted using logistic regression analysis that includes treatment arm and any baseline variables that are imbalanced between the arms as explanatory variable.

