 - 1 The PRO-CTCAE assessment is required for all patients. If the PRO-CTCAE assessment completed prior to registration is obtained \leq 14 days prior to treatment, then the PRO-CTCAE assessment on day 1 of cycle 1 may be skipped. The PRO-CTCAE patient-completed booklet for this protocol can be found on the 'CIRB Approved Documents' tab on the CTSU website.
 - 2 To be completed after registration and \leq 21 days prior to treatment.
 - 3 For women of childbearing potential. Must be done \leq 14 days prior to initiation of study treatment.
 - 4 See Section 6.2.

- 5 Baseline scans can include either: 1) a CT, spiral CT, or MRI and bone scan, or 2) an FDG-PET scan and diagnostic CT performed with both IV and oral contrast, and the CT acquired with 5 mm or less slice thickness. Supporting documentation is to be submitted, per Section 6.1.1.
- 6 ECG prior to registration should be performed if clinically indicated.
 - A All patients receiving immunotherapy will have a urinalysis or urine protein performed \leq 72 hours prior to every dose. If urine protein is \geq 2+, 24-hour urine collection or UPC ratio will be required.
 - B Required only if signs or symptoms suggestive of metastases develop.
 - C \leq 2 days prior to each treatment if accessible to physical examination.
 - D Every 3 months until evidence of progression or relapse. If the baseline scans were a CT or MRI and bone scan, follow-up bone scans are required only for patients with bone metastases as the only site of evaluable disease, and are optional for other patients. Response assessment should include assessment of all sites of disease and use the same imaging method as was used at baseline. Bone imaging (after baseline) is required only if indicative of metastases at baseline or if signs or symptoms suggestive of metastases develop.

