11.0 MEASUREMENT OF EFFECT

Disease should be re-evaluated every 12 weeks after C1D1. Disease response will be made by institutional investigator assessment, based on local radiology review and RECIST v1.1 criteria. Refer to the Study Calendar to determine the allowable scan windows ([Section 5.0](#)). This study uses iRECIST guidelines to guide treatment beyond progressive disease. Irradiated lesion will not be included in RECIST v1.1 or iRECIST evaluation.

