11.4 Evaluation of Best Overall Response

The best overall response is the best response recorded from the start of the treatment until disease progression/recurrence (taking as reference for progressive disease the smallest measurements recorded since the treatment started). The patient's best response assignment will depend on the achievement of both measurement and confirmation criteria (see [Section 11.6.1](#))

For Patients with Measurable Disease (i.e., Target Disease)

Target Lesions	Non-target Lesions	New Lesions	Overall Response	Best Overall Response when Confirmation is Required
CR	CR	No	CR	≥ 4 wks confirmation*
CR	Non-CR/Non-PD	No	PR	
CR	Not evaluated	No	PR	≥ 4 wks confirmation*
PR	Non-CR/Non-PD/not evaluated	No	PR	
SD	Non-CR/Non-PD/not evaluated	No	SD	Documented at least once ≥ 4 wks from baseline*
PD	Any	Yes or No	PD	
Any	PD**	Yes or No	PD	No prior SD, PR or CR
Any	Any	Yes	PD	

* Only for non-randomized trials with response as the primary endpoint.

** In exceptional circumstances, unequivocal progression in non-target lesions may be accepted as disease progression.

Note: Patients with a global deterioration of health status requiring discontinuation of treatment without objective evidence of disease progression at that time should be reported as "symptomatic deterioration" on the Off-treatment Form (C-300) under "other." Every effort should be made to document the objective progression even after discontinuation of treatment.

For Patients with Non-measurable Disease (i.e., Non-target Disease)

Non-Target Lesions	New Lesions	Overall Response
CR	No	CR
Non-CR/non-PD	No	Non-CR/non-PD*
Not all evaluated	No	not evaluated
Unequivocal PD	Yes or No	PD
Any	Yes	PD

'Non-CR/non-PD' is preferred over 'stable disease' for non-target disease since SD is increasingly used as an endpoint for assessment of efficacy in some trials so to assign this category when no lesions can be measured is not advised.

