13.7 Secondary Analysis Plans

A key secondary analysis will be to repeat the primary analysis that defines a tumor response by central review using iRECIST criteria.

For the secondary time-to-event endpoints, stratified Cox models will be used to compare the outcomes between the two treatment groups. This includes PFS and OS. The subgroup analyses will be done using a stratified Cox model that includes the treatment arm assignment as an explanatory variable and a separate model will be generated for each level for the subgroup of interest. The results will be summarized with a forest plot displaying the estimate of the hazard ratio and corresponding 95% confidence interval.

The rates of treatment discontinuation at one year will be summarized with a binomial point estimate and corresponding 95% confidence interval by arm. The denominator will be all patients randomized to the treatment arm and who are still alive and progression-free at one year and the numerator will be the number of patients who are alive and progression-free at one year and discontinued the protocol

treatment prior to one year. A comparison between the rates will be performed with a chi-square test or a Fisher's exact test if the assumptions of the chi-square test are violated.

Adverse events will be summarized with frequencies and relative frequencies. The maximum grade for an AE will be recorded for each patient by treatment arm. The number (percent) of patients that experience each observed adverse event will be summarized by treatment arm. In addition, the proportion of patients that experience a grade 3+, grade 4+, and grade 5 adverse event will be summarized as the number and percent of patients by treatment arm. The primary summary will be regardless of attribution. We will also do an analogous summary of the adverse events that were deemed at least possibly related to treatment.

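### The primary response test excludes randomized patients who are not evaluable, but the term is undefined and no all-randomized response analysis is stated

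*Combined protocol and SAP*

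**What the plan says.** Section 13.2.1 defines the endpoint: "The primary endpoint is tumor response within 6 months of randomization". Response means CR or PR by RECIST 1.1, as judged by the treating physician.

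Section 13.6 then fixes who is analysed: "The analysis will be a modified intent-to-treat analysis where patients are ineligible or not evaluable will be excluded". The timing uses the same term: "The final analysis will occur after 136 evaluable patients have completed 6 months of follow-up". Section 13.4 budgets for the loss: "The sample size will be inflated by 5% to account for ineligible or non-evaluable patients, so the target accrual is 144 patients".

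The iRECIST analysis in Section 13.7 takes over the same set: "A key secondary analysis will be to repeat the primary analysis that defines a tumor response by central review using iRECIST criteria".

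On assessment, Section 11.0 states: "Disease should be re-evaluated every 12 weeks after C1D1". Section 13.1 describes the trial as open-label.

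**The concern.** A patient may be randomized and then die early, deteriorate clinically, withdraw or never start treatment, all before any post-baseline assessment. Such a patient has no documented response and is probably a treatment failure. The plan permits two readings. Under Section 13.2.1 the patient did not respond within 6 months and counts in the denominator. Under Section 13.6 the patient may be not evaluable and leave the denominator. Two competent analysts could therefore obtain different primary p-values from the same data.

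The design makes the choice matter. Treatment is known, only Arm B has an added treatment, and the first scheduled scan is 12 weeks after C1D1. If the reasons for having no assessment differ by arm, exclusion after randomization breaks the comparison that randomization set up. PFS and OS (Section 13.2.2) do count early deaths, but they are secondary.

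**Working it through.** **1. The plan's own figures.** Inputs from Section 13.4: one-sided alpha 0.10, power 90%, response 20% versus 40%. With pooled variance and mean rate 0.30:

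n per arm = [1.2816 × √(2 × 0.30 × 0.70) + 1.2816 × √(0.20 × 0.80 + 0.40 × 0.60)]² / 0.20² = (1.2816 × 1.2805)² / 0.04 = 67.3, so 68 per arm and 136 in total.

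136 / 0.95 = 143.2, so 144. Both figures reproduce; the sample size is not in question. The margin between accrual and the trigger for the final analysis is 144 − 136 = 8 patients.

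**2. Does any other section supply the definition?**
- Section 11.4: in the best-response table for measurable disease, *not evaluated* is only an entry for non-target lesions. As an overall result it appears only in the table for non-measurable disease, and Section 3.2.3 requires measurable disease.
- Section 11.4 also foresees patients who stop for symptomatic deterioration without objective progression. It does not say how they enter the response rate.
- Section 12.5 defines ineligible patients and requires no follow-up of never-treated patients. It does not define evaluability.
- Section 14.1.4 promises intent-to-treat, but only for the quality-of-life substudy.
- Section 13.6 adds a logistic regression and names no population for it.

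None of these closes the gap.

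**3. Effect on the test if the excluded patients are non-responders.** Assumptions: 72 randomized per arm, true response 20% in both (14.4 expected responders per arm), and k non-responders excluded, so the evaluable rate is 14.4 / (72 − k). The calculation is an exact binomial enumeration with an unstratified pooled z test at one-sided 0.10. It applies the futility stop at half the patients when the Arm A rate exceeds the Arm B rate. The documents give no split by arm; those below are assumed.

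| Excluded A/B | Evaluable rates A, B | One-sided type I error |
|---|---|---|
| 0/0 | 20.0%, 20.0% | 0.098 |
| 4/4 | 21.2%, 21.2% | 0.096 |
| 2/6 | 20.6%, 21.8% | 0.126 |
| 0/8 | 20.0%, 22.5% | 0.165 |
| 6/2 | 21.8%, 20.6% | 0.071 |
| 8/0 | 22.5%, 20.0% | 0.051 |

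Equal exclusion leaves the size alone but raises the reported rates: at 4/4, true rates of 20% and 40% appear as 0.20 × 72/68 = 21.2% and 0.40 × 72/68 = 42.4%.

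**4. One data set, two answers.** 14/72 versus 19/72: difference 0.0694, pooled rate 33/144 = 0.229, standard error 0.0700, z = 0.99, one-sided p = 0.161. Exclude seven Arm B non-responders, giving 14/72 versus 19/65: difference 0.0979, pooled rate 33/137 = 0.241, standard error 0.0732, z = 1.34, p = 0.091. The second crosses 0.10.

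**5. The opposite assumption.** If loss is unrelated to response, non-responder counting lowers the observed rate to 0.20 × (72 − k)/72. Same enumeration:

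| Lost A/B | Size, exclusion | Size, non-responder counting |
|---|---|---|
| 6/2 | 0.098 | 0.131 |
| 8/0 | 0.100 | 0.170 |
| 0/8 | 0.091 | 0.052 |

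**6. Power.** If 20% and 40% are rates in evaluable patients and 5% are lost equally, exclusion (68 per arm) has 89.9% power. Counting the lost as non-responders (72 per arm, 19% versus 38%) has 89.3%.

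**The case against.** The strongest reply is that non-responder counting is no safer in general. Step 5 bears this out: when loss is unrelated to response and heavier in Arm A, it is the rule that inflates type I error. In an open-label trial, control-arm patients who decline treatment would be scored as failures, to Arm B's advantage. This stands, and it is the reason to report both analyses.

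Second, the splits are chosen. If each of 8 exclusions were equally likely to fall in either arm, 0/8 would have probability 1/256 = 0.4%, and 6 or more in Arm B 37/256 = 14%. That also stands: the figures show sensitivity and are not a forecast.

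Third, the exclusion is disclosed, and one 5% allowance covers ineligible and non-evaluable patients together, which suggests that a small group was meant. Assessment before week 12 is also possible. The study calendar allows tumor measurement "2 days prior to each treatment if accessible to physical examination", and Section 11.4 asks of patients who stop for deterioration: "Every effort should be made to document the objective progression even after discontinuation of treatment". These points make wide exclusion less likely, but an inflation factor is not an analysis rule.

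A reader might go further and infer that the plan drops early deaths, that it favours Arm B, or that the treating physician decides who is evaluable. The documents support none of these. They do not say whether an early death is evaluable or who decides, and the bias could run either way. Nor do they rule out an all-randomized analysis, since the logistic regression has no stated population. The supportable statement is that none is stated.

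**Conclusion.** The point holds as a gap in the definition of the primary analysis set, and it should be fixed before analysis. The plan excludes patients after randomization under an undefined term, leaves those without a post-baseline assessment unclassified, and states no all-randomized response analysis as a check. The iRECIST analysis inherits the same set.

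Within the plan's own margin of 8 patients, type I error ranges from 0.051 to 0.165 over the splits examined. It stays near 0.10 when exclusions are balanced. That range rests on assumed splits, on every excluded patient being a non-responder, and on an unstratified approximation to the Mantel-Haenszel test. It measures exposure and does not show that bias will occur.

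**What to change.** In Section 13.6:
- Exclude only patients found ineligible on baseline facts, by a review blind to arm and outcome.
- Count every other randomized patient without a documented CR or PR within 6 months as a non-responder.
- Define *evaluable*, and keep the evaluable-only analysis as a sensitivity analysis.
- Report exclusions and missing assessments by arm, with reasons.

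Use the same set for the iRECIST analysis in Section 13.7, and word the trigger for the final analysis to match.

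At minimum, define the term so that early death, deterioration or the absence of a scan does not make a patient not evaluable. Then add an all-randomized response analysis beside the primary one.

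The change is wording and needs no more patients. It lowers the reported response rates and costs about 0.6 points of power at 5% loss. The new rule can itself mislead when losses are unequal and unrelated to response, so the evaluable-only result should be shown with it.

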1.2 Registration Patient Reported Outcomes (PROs) and Quality of Life (QOL) Measurements

PROs, particularly involving symptomatic toxicities, provide discrepant yet complementary information compared with clinician interpreted data^{12–16}. In particular, greater sensitivity for adverse event reporting, auxiliary characterization of performance status and earlier detection of symptoms^{12,14,17–20}. Implementation of PRO systems has shown feasibility in the clinical trial setting demonstrating 78% to 96% adherence^{21,22} and several studies report that baseline PRO and QOL data may prognosticate survival better than performance status in clinical trials^{23–25}. A landmark prospective study also now suggests that serial monitoring of patient reported symptoms may improve median overall survival by up to 5 months for patients undergoing treatment of solid malignancies²².

QOL measurements of fatigue and overall perception of QOL are routinely included in Alliance studies and will be assessed upon registration in this study. Baseline single-item assessments of fatigue and overall QOL are strong prognostic indicators for survival in cancer patients, independent of performance status^{26–28}. Routine inclusion of these measures should be considered similar to that of including performance status, either as stratification or prognostic covariates.

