4.6.2 Treatment Assignments

Patients will be randomized 1:1 to the two treatment arms. The factors defined in [Section 4.8.1](#) will be used as stratification factors.

After the patient has been registered into the study, the values of the stratification factors will be recorded, and the patient will be randomized to one of the following treatment groups using the Pocock and Simon dynamic allocation procedure which balances the marginal distributions of the stratification factors between the treatment groups.

- 1) Immunotherapy
- 2) Immunotherapy + Single Site Radiotherapy

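### The supporting logistic model in Section 13.6 picks covariates by undefined observed imbalance, so the randomisation factors will almost never enter and prognostic variables enter only by chance

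*Combined protocol and SAP*

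**What the plan says.** Section 13.6 (Primary Analysis Plan) compares response rates with a Mantel-Haenszel test that takes account of the randomisation factors. It then describes an additional logistic regression that "includes treatment arm and any baseline variables that are imbalanced between the arms as explanatory variable". It does not say which baseline variables are candidates, how imbalance is judged, how many variables may enter, or whether any must enter.

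Section 4.6.1 names two stratification factors, platinum status and visceral metastasis. Section 4.6.2 allocates patients 1:1 by the "Pocock and Simon dynamic allocation procedure which balances the marginal distributions of the stratification factors" between the arms.

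Section 1.2 describes baseline fatigue and overall QOL as prognostic for survival and says: "Routine inclusion of these measures should be considered similar to that of including performance status, either as stratification or prognostic covariates". Section 14.1.4 names stratification and prognostic factors as possible covariates, but only for the QOL mixed model. Sections 13.1 and 13.2.1 make the trial open-label, with response judged by the treating physician.

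**The concern.** Under randomisation, an observed imbalance is a chance event. What adjustment gains depends on how strongly a variable predicts response, not on whether it happens to differ between arms. A rule based on imbalance therefore selects on the wrong property.

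Two consequences follow. First, the factors that the allocation deliberately balances are the ones least likely to be selected, so the supporting model will usually omit what the primary test accounts for. Second, because imbalance is undefined and the candidates are not listed, two analysts could fit different models to the same data and both follow the plan. In an open-label trial with physician-assessed response, covariates chosen after the data are seen are an avoidable weakness. At stake is the value of this analysis as support for the primary result.

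**Working it through.** **The plan's own figure.** Inputs from Section 13.4: "one-sided alpha = 0.10", power 90%, response 20% in Arm A and 40% in Arm B. With pooled variance under the null and no continuity correction:

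n per arm = [z(0.90)·√(2·p̄·(1−p̄)) + z(0.90)·√(pA(1−pA) + pB(1−pB))]² / (pB−pA)², with p̄ = 0.30

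= [1.2816·√0.42 + 1.2816·√0.40]² / 0.04 = (1.2816 × 1.2805)² / 0.04 = 67.3, rounded up to 68.

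The total is 136, and 136/0.95 = 143.2 gives 144. Both figures match the plan. Nothing below changes them.

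**How often variables are flagged.** Taking imbalanced to mean two-sided p<0.10 (an assumption, since the plan gives no criterion), the chance that at least one of k independent variables is flagged is 1 − 0.9^k: 41% for k=5, 65% for k=10 and 79% for k=15. If the allocation keeps two of ten variables balanced, k=8 applies, giving 57%.

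**Simulation.** 136 patients, 3,000 trials per scenario, no futility look. Assumptions not in the documents:
- Pocock-Simon allocation with a biased coin of 0.8
- ten binary baseline variables: two stratification factors, three prognostic, five noise
- an odds ratio of 2 or 3 for each stratification and prognostic factor
- intercepts set so that marginal response is 20% or 40%

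A variable is flagged if |difference in proportions| / SE > 1.645. Success means the Wald statistic for arm exceeds 1.2816.

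| Model | Power, OR 2 | Power, OR 3 | Type I error, OR 2 | Type I error, OR 3 |
|---|---|---|---|---|
| Imbalance-selected | 0.904 | 0.914 | 0.093 | 0.090 |
| Arm + stratification factors | 0.916 | 0.928 | 0.101 | 0.105 |
| Arm + stratification + three prognostic | 0.923 | 0.951 | 0.099 | 0.101 |

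- A stratification factor was selected in 0 of 3,000 trials in every scenario.
- A given prognostic variable was selected in about 10% of trials, so it was omitted in about 90%.
- At least one variable was selected in about 57% of trials. In the other 43% or so the model reduces to arm alone.
- Power gap against stratification factors only: 0.916 − 0.904 = 1.2 points and 0.928 − 0.914 = 1.4 points.
- Power gap against the fuller model: 0.923 − 0.904 = 1.9 points and 0.951 − 0.914 = 3.7 points.

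**Sensitivity to the assumptions.** These runs used 1,500 trials per scenario and ten variables, three of them prognostic with log-odds ratios per SD as shown. Prespecified adjustment used exactly the prognostic variables.

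| Log-odds ratios | Prespecified | Imbalance-selected | Gap (points) |
|---|---|---|---|
| 0.7, 0.7, 0.5 | 94.6% | 90.9% | 3.7 |
| 0.7, 0.7, 0.5 (independent repeat) | 93.4% | 90.9% | 2.5 |
| 0.3, 0.3, 0.2 | 91.1% | 89.7% | 1.4 |

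Runs of the model recommended below (randomisation factors plus performance status), again with assumed strengths, gave about 1 to 3 points more power, and type I error of about 0.10 against 0.087 to 0.094 for the imbalance-selected model.

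**Monte Carlo error.** For a type I error near 0.10 with 3,000 trials it is √(0.10·0.90/3000) = 0.0055. The shortfall of 0.007 to 0.010 in the main simulation is thus 1.3 to 1.8 standard errors.

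**Room for covariates.** Expected responders are 68·0.20 + 68·0.40 = 13.6 + 27.2 = 40.8 under the design alternative and 136·0.20 = 27.2 under the null. Arm plus three binary covariates is four terms: 40.8/4 = 10.2 or 27.2/4 = 6.8 responders per term. Adding fatigue and QOL makes six terms: 6.8 or 4.5.

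**The case against.** The strongest reply is that this model decides nothing. The primary test already accounts for the stratification factors, PFS and OS use stratified Cox models (Section 13.7), and the logistic regression carries no alpha, decision rule or sample size. Asking whether a result survives adjustment for observed imbalance is a familiar sensitivity question. All of that stands, and it limits the point to the supporting analysis.

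A reader might infer four stronger things that the documents do not support:
- **That the rule excludes stratification and prognostic factors by design.** It excludes nothing; any imbalanced variable enters. The randomisation factors drop out in effect, and prognostic variables are simply not guaranteed.
- **That the adjusted estimate loses precision.** In logistic regression, adding prognostic covariates raises the standard error of the log-odds ratio. In the 0.7, 0.7, 0.5 repeat the mean standard error was 0.462 with prespecified adjustment and 0.409 with imbalance selection. The gain is in power, because the conditional effect is larger.
- **That false positives are inflated.** No run shows material inflation. The imbalance-selected model gave 8.3% in one set of runs, 8.7% to 9.4% in others, and 9.9% to 10.8% in the repeat.
- **That Section 1.2 requires fatigue and QOL in this model.** It says their inclusion should be considered, and the prognosis it cites is for survival, not tumour response.

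It is also fair that fatigue and QOL cannot simply be mandated. Footnote 2 of the Study Calendar has the form completed after registration, while Appendix I places it at registration. Randomisation follows registration and the trial is open-label, so the scores may be recorded once the arm is known.

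**Conclusion.** The point holds for the additional logistic model only. Its covariates are chosen by an undefined criterion unrelated to prognostic value. Minimisation keeps platinum status and visceral metastasis out in practice, and prognostic variables enter only by chance, so the supporting model will usually be less adjusted than the primary test.

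The cost is small: about 1 to 4 points of power against prespecified adjustment, with a test that is slightly conservative in most runs. These figures rest on assumed prognostic strengths, an assumed p<0.10 criterion and an assumed number of candidate variables; the documents give none of them. That the randomisation factors are almost never selected depends much less on these choices, because it follows from the allocation method. The primary test, alpha and sample size are unaffected.

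**What to change.** Replace the imbalance rule in Section 13.6 with a prespecified logistic model containing treatment arm, platinum status, visceral metastasis and pre-registration ECOG performance status (0-1 versus 2). Performance status is already on the Study Calendar before registration. Keep any imbalance-driven model as exploratory only.

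Add baseline fatigue and overall QOL only if footnote 2 of the Study Calendar and Appendix I are reconciled so that the scores are recorded before the arm is known. In that case, also state how missing scores are handled, since a complete-case fit would drop those patients.

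The cost is one sentence, best settled before the interim comparison of arms. No new data are needed for the four-term model. There are two small downsides: with about 27 to 41 expected responders the list must stay short, and the odds ratio must be reported as conditional on the covariates.
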